The recovery (management and rehabilitation) processes from substance use disorders are not inclusive enough and confine members to physical attendance for the purpose of detoxification, neglecting the important factors such as life skills, social, cultural, economic, environmental, and family factors. Since after detoxification of the substances users return to their family and society, there can't be expect a perfect quit without considering these factors carefully (Jepkorir, 2023).

Life skill educational program to enhance self-efficacy as a preventive approach in which it focuses on the development of personal and social skills. Previous studies revealed that there were few studies about the effects of life skills training on relapse prevention among patients with substances use disorders

(Volkow, 2020). Therefore, the present study is an attempt to introduce a safe and reasonable training program that help patients with substance use disorders to enhance abstinence self-efficacy.

Aim of the study

The study aims: to evaluate the effect of life-skills training program on self-efficacy among patients with substance use disorders.

The aim of this study will be achieved through the following objectives:

- 1- Assessing self-efficacy among patients with “substance use disorders”.
- 2- Assessing risk for relapse among patients with “substance use disorders”.
- 3- Developing life skills training program for self-efficacy among patients with substance-use disorders based on identified their needs.
- 4- Implementing the developed life skills training program of relapse prevention among patients with substance-use disorders.
- 5- Evaluating the effect of implementing life skills training program on self-efficacy among patients with “substance-use disorders”.

Research Hypothesis

Life skills training program will have a positive effect on self-efficacy among patients with substance-use disorders.

Subjects & Methods

Study design

A quasi-experimental research design on one group (pre-post) test will be used to conduct the current study.

Study setting

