The study will be conducted at Alabbasya Mental Health Hospital in Cairo. It is the oldest and biggest hospital for psychiatric illnesses in Egypt, affiliated to General Secretariat of Mental Health and Addiction Treatment of the Ministry of Health. It was established in 1883 A.D over an area of 68 acres. Its capacity is 1950 beds. The hospital structure is divided into such as, sections: Twenty-one old free sections, four illegal sections (forensic), two new buildings one of them for males that included addiction treatment and rehabilitation department in new building (2nd -3rd -4th) floor included detox ward about 30 bed, rehabilitation ward 60 bed, and dual ward, and another one for females. also, clinics such as, outpatient clinic - addiction clinic - children clinic - adolescent clinic - daycare

clinic - aging clinic - dental clinic - electroencephalogram clinic and electro compulsive therapy clinic.

Subjects

A purposive sample will be obtained from patients with “substances use disorders” who meet inclusion criteria during their existence in the previously mentioned setting.

Inclusion criteria:

- Age: from 20 years to 50 years.
- Had history of one episode of relapse
- Free from any physical disease such as diabetes, hypertension, viral hepatitis etc.)
- Free from other Psychiatric disorders.

Sample size

Based on power analysis; Type I error (α) =0.05 with confidence level (1- α) =0.95 and Type II error (β) = 85%, by power test (1- β) =0.15, sample size was

calculated according to the following equation that has been adopted from (Gupta, et al, 2016)

$$N= 2(Z_{\alpha} + Z_{[1-\beta]})^2 \times SD^2/d^2$$

Where: n is the sample size, Z_{α} and $Z_{(1-\beta)}$ are constant values for convention values of α and β values where $Z_{\alpha} = 1.96$ when $\alpha = 0.05$ and $Z_{(1-\beta)} = 1.036$ when $\beta = 0.20$, SD is the standard deviation obtained from previous study Moshki, et al., (2014) and d is the effect size.

$$N= 2(1.96 + 1.03)^2 \times 7.7^2/5^2 = 42.4$$

Therefore, the minimal sample size was found to be =50 participants

Tools of data collection

Tool I: Interview Questionnaire

It will be designed by the researcher and reviewed by supervisors. It will be written in the Arabic language for gathering data in relation to the following parts:

Patients' characteristics. such as age, marital status, residence, qualifications, starting and years of substance use.... etc.

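### The one-group pre-post study is sized with the per-group formula for two independent means, so 42.4 and its power are not derived for this design; the error is conservative on the protocol's own inputs

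*Protocol*

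**What the plan says.** Protocol, Study design: "A quasi-experimental research design on one group (pre-post) test will be used to conduct the current study". No comparison group is planned.

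Protocol, Sample size: the formula is "N= 2(Z_{\alpha} + Z_{[1-\beta]})^2 \times SD^2/d^2", evaluated as "N= 2(1.96 + 1.03)^2 \times 7.7^2/5^2 = 42.4". The section then sets a minimum of 50 participants, without explaining the step up from 42.4. The SD is said only to come from an earlier study, which the reference list describes as life-skills training in university students. The section does not say whether 7.7 is the SD of a score at one time or of a within-patient change. It gives no pre-post correlation.

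The power target is not printed consistently. One sentence reads "Type II error (β) = 85%, by power test (1- β) =0.15", and a later one attaches Z = 1.036 to β = 0.20. A Z of 1.036 belongs to 85% power, so 85% is taken as the intention here; that is an inference.

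Protocol, Tool II: the self-efficacy total runs from 40 to 200.

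**The concern.** The leading 2 in the printed formula is the variance factor for a difference between two independent means, and the result is a number per group. In a one-group pre-post study each patient is his or her own comparator. Precision then depends on the SD of the within-patient change, which depends on how strongly the two scores are correlated. The protocol states neither quantity.

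The sample-size section is the only justification the protocol gives for its number of patients, and it refers to a comparison the study will not make. At stake is whether 50 is enough, and whether a reader can tell from the text what 50 can detect.

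**Working it through.** **Inputs from the Sample size section.** SD = 7.7, d = 5, α = 0.05 with Zα = 1.96 (so two-sided), Zβ = 1.036 (1.03 in the printed arithmetic), planned N = 50. The pre-post correlation ρ is not given, so an assumed range is shown.

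**1. The printed figure.** 2 × (1.96 + 1.03)² × 7.7² / 5² = 2 × 8.9401 × 59.29 / 25 = 42.40. It reproduces. With Zβ = 1.036 it is 42.58, which rounds up to 43. The arithmetic is right; the formula is the per-group one for two independent means.

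**2. The formula for this design.** n = (Zα + Zβ)² × SDchange² / d², with SDchange = SD × √(2(1 − ρ)). At ρ = 0, SDchange² = 2 × SD² and the printed formula is recovered. At any other ρ the two differ.

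**3. If 7.7 is already the SD of change.** (1.96 + 1.036)² × 59.29 / 25 = 8.976 × 2.3716 = 21.3, so 22 patients, or 24 by the exact (noncentral) t calculation. This is half the printed figure. Power with 50 pairs is 99.4%.

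**4. If 7.7 is the SD at one time point.**

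| Assumed ρ | SDchange | n for 85% power, normal approximation | n, exact t | Power with 50 pairs (paired t) |
|---|---|---|---|---|
| −0.2 | 11.93 | 51.1 (52) | 54 | 82.8% |
| 0 | 10.89 | 42.6 (43) | 45 | 88.9% |
| 0.3 | 9.11 | 29.8 (30) | 32 | 96.7% |
| 0.5 | 7.70 | 21.3 (22) | 24 | 99.4% |
| 0.7 | 5.96 | 12.8 (13) | 15 | above 99.9% |

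**5. What a given number of complete pairs delivers, whatever the SD.** For a two-sided 5% paired t test at 85% power, the detectable mean change is 0.432 SDchange with 50 pairs, 0.457 with 45 and 0.486 with 40.

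**6. Where 50 stops being enough.** From step 5, d = 5 is detectable with 50 pairs while SDchange is at most 5 / 0.432 = 11.57. With SD = 7.7 this means ρ no lower than 1 − 11.57² / (2 × 59.29) ≈ −0.13.

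**7. Sensitivity to the SD itself.** If the SD of change on the 40–200 total were 15 or 20 points (values assumed for illustration), 50 pairs would give about 64% or 41% power for a 5-point change.

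**The case against.** The strongest reply is that nothing is lost. On the protocol's d and SD, the two-group formula asks for at least as many patients as the paired one at any non-negative correlation, and 50 exceeds even the ρ = 0 requirement of 43 (45 by exact t). This stands, and it is why the point is a correction to the justification and not to the enrolment.

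Four stronger readings are tempting, and the documents do not support them:

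- **An under-sized trial.** A reader might double 43 per group to 86 and see a shortfall against 50. No second group is planned, so no such shortfall exists.
- **An unpaired analysis.** A reader might infer from the formula that the pre and post scores will be compared as independent samples. The protocol (Administrative design) names only the software and no test, the analysis plan is not at hand, and a planning formula does not prescribe an analysis.
- **Power that misses 85% because of the formula.** A reader might compare the powers at 50 patients with the 85% target. That target belongs to 42.4. At ρ = 0, where the formulas coincide, the 88.9% reflects the unexplained step from 42.4 to 50; the printed two-group formula at 50 per group would itself give about 90%.
- **A trial with 99% power.** The high powers in the working show direction only. They hold if 7.7 and 5 apply to this outcome in these patients, which the protocol does not establish.

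**Conclusion.** The mismatch between formula and design is certain from the protocol's own text. The 42.4 and the inferred 85% power are not derived for a one-group pre-post comparison. With d = 5, the requirement for the design actually planned lies anywhere from about 13 to 43 patients for correlations between 0.7 and 0, and is about 22 if 7.7 is the SD of change.

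The error is conservative on these inputs. With 50 complete pairs the target is met for any non-negative correlation, and only a negative one (below about −0.13) makes 50 too few. This rests on 7.7 being a relevant SD on the 40–200 total, on 85% being the intended power, and on complete pairs. Withdrawal is allowed at any time and the 5 pilot patients may be excluded, so the number of pairs could be below 50. Should-fix.

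**What to change.** In the Sample size section:

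- Replace the formula with n = (Zα + Zβ)² × SDchange² / d², where SDchange = SD × √(2(1 − ρ)).
- State SDchange on the 40–200 total, or the SD and the assumed ρ, with the source. Say what kind of SD 7.7 is and on which scale.
- Correct the power labels so that α, β, power and Z agree.
- Keep N = 50 and state what it delivers: 85% power, two-sided 5% paired t test, for a mean change of 0.43 SDchange with 50 complete pairs, 0.46 with 45 and 0.49 with 40. This also makes visible how much loss of pairs 50 allows for.

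The cost is a rewritten paragraph and one sourced assumption. Enrolment, outcome and visits are unchanged.

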Clinical data (addiction History). about substances as types of substance, onset, duration, route, etc.

Tool II: Alcohol Abstinence Self-Efficacy Scale (AASE)

It was adapted by the researcher from DiClemente et al., (1994) to assess personal confidence against taken substance. It consists of 40 items for assessing self-efficacy. It includes 4 domain parts unranked: negative effect (1-5-9-13-17-21-25-29-33-37), social/positive situations (2-6-10-14-18-22-26-30-34-38), physical and other concern (3-7-11-15-19-23-27-31-35-39), and craving and urges(4-8-12-16-20-24-28-32-36-38). Every domain includes 10 items.

Scoring system. Each statement was rated on 5 points as a Likert Skill Scale ranged by statistical from (1) No Confidence, (2) Low Confidence, (3) Middle Confidence, (4) High Confidence, and (5) Excellent Confidence. The total score ranged from 40:200 ranged as, Low self-efficacy $40 < 120$, Middle self-efficacy $121 < 160$, and High self-efficacy $161 < 200$.

Validity:

The one tool will be formulated and submitted to (5) experts in psychiatric and mental health nursing or other specialty who will review the content of the tools for their comprehensiveness, accuracy, clarity, and relevance.

Reliability:

Cronbach's Alpha will be used to determine the internal reliability of the tool.

Preparatory Phase

This phase will be included reviewing of literature related to substance use disorder, relapse prevention, this served study tools for data collection. During this phase, the researcher also will be visited the selected place to be acquainted with the staff and the study settings.

Ethical considerations:

Research approval obtained from the faculty of Nursing- Ain Shams University Ethical Committee before starting the study. The researcher explained the aim and objectives of the study to patients with substance use disorder included in the study before starting. Written approval obtained from patients with substance use disorders before inclusion in the study. They guarantee that all the gathered data will be used confidentially and will be used for research purposes only. The researcher maintain anonymity and confidentiality of subjects' data included in the study. Patients with substance use disorder will be informed that they allow for withdrawal from study at any time.

Administrative design

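### The printed AASE scoring key assigns item 38 to two domains and item 40 to none, so the craving/urges score is wrong if the key is followed; the total is affected only if it is built from the domain scores

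*Protocol*

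**What the plan says.** The key stands in the protocol under Tool II: Alcohol Abstinence Self-Efficacy Scale (AASE). On the length of the scale the protocol says "It consists of 40 items for assessing self-efficacy", and on its structure "Every domain includes 10 items". The four domains are keyed as follows:

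- "negative effect (1-5-9-13-17-21-25-29-33-37"
- "social/positive situations (2-6-10-14-18-22-26-30-34-38"
- "physical and other concern (3-7-11-15-19-23-27-31-35-39"
- "craving and urges(4-8-12-16-20-24-28-32-36-38"

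On scoring it says "Each statement was rated on 5 points as a Likert Skill Scale", with responses from 1 to 5, and "The total score ranged from 40:200". The low, middle and high bands are defined on that total. The key is printed once, and nothing elsewhere in the protocol repeats or corrects it.

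**The concern.** Four domains of 10 items can cover a 40-item scale only if every item belongs to exactly one domain. The printed key breaks this: one item is used twice and one is answered but assigned nowhere.

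Self-efficacy is the subject of the aim and of the only hypothesis, and Tool II is the only self-efficacy instrument that the protocol describes. Its key is what someone writing the SPSS scoring would copy. If it is copied as printed:

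- the craving/urges score contains the wrong tenth item at both assessments;
- a Cronbach's alpha for that domain, if one is computed, uses the wrong item;
- two domains share an item, which builds some artificial overlap into their scores;
- a total obtained by adding the domains counts item 38 twice and omits item 40.

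The simplest checks would not reveal the slip, because the count per domain and the range of the total both come out as stated.

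**Working it through.** **Inputs**, all from the Tool II section: 40 items, four domains of 10, the four printed lists, responses from 1 to 5, and a total from 40 to 200.

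**Step 1: count the entries.**

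| Domain | Entries | First to last | Steps between entries |
|---|---|---|---|
| Negative effect | 10 | 1 to 37 | 4 throughout |
| Social/positive situations | 10 | 2 to 38 | 4 throughout |
| Physical and other concern | 10 | 3 to 39 | 4 throughout |
| Craving and urges | 10 | 4 to 38 | 4 up to item 36, then 2 |

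There are 10 + 10 + 10 + 10 = 40 entries. Item 38 occurs twice, so there are 40 − 1 = 39 distinct items. The only number from 1 to 40 that does not occur is 40. The stated 40 items are therefore not reproduced by the key.

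**Step 2: test the obvious correction.** With the last craving/urges entry read as 40, the four lists cover items 1 to 40 exactly once, and every list steps by 4 throughout. Both stated figures, 40 items and 10 per domain, are then met.

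**Step 3: error in the domain score.** Let x38 and x40 be one patient's answers at one assessment.

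- Printed craving/urges score − corrected score = x38 − x40.
- Each answer lies between 1 and 5, so the error lies between 1 − 5 = −4 and 5 − 1 = +4.
- The domain score runs from 10 × 1 = 10 to 10 × 5 = 50, a width of 40, so the extreme error is 4/40 = 10% of that width.

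**Step 4: error in the pre-post comparison.** Bias in mean change = mean(change in x38) − mean(change in x40). It is zero if the two items shift equally on average. The protocol gives no item-level data, so neither its size nor its sign can be estimated.

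**Step 5: error in the total.**

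- Summed directly over items 1 to 40: error 0.
- Summed over the four printed domains: error x38 − x40, the same as in Step 3.

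**Step 6: why routine checks pass.** Each printed list has 10 entries. Forty entries scored 1 to 5 give a minimum of 40 × 1 = 40 and a maximum of 40 × 5 = 200, whether or not one item is repeated. Only an item-by-item check, or a comparison of the domain sum with the direct total, shows the fault.

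**The case against.** The strongest reply is that this is a visible typing slip with limited reach. The pattern of fours and the single unassigned item show what was meant. Item-level answers are collected in any case, so a mis-scored domain could be recomputed without loss. No hypothesis, cut-off or analysis is stated for a domain: the hypothesis concerns self-efficacy overall, and the bands are set on the total. All of this stands, and it makes the correction minor. It does not make the printed rule right, since the key is the protocol's only instruction for scoring the domains.

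Three stronger readings are tempting, and the protocol supports none of them.

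- **That the main outcome is wrong, or that only 39 of the 40 items are used.** For a 40-item scale with each item rated 1 to 5 and a total of 40 to 200, the natural total is the direct sum, which uses every item. Nothing says that the total is built from domain scores. Changes of category near the band limits depend on the same unstated step.
- **That an error of up to 4 points rivals the difference of 5 in the sample-size calculation.** The 4 is an extreme for one patient at one assessment. The 5 is a mean difference, paired with an SD of 7.7 from an earlier study whose listed title concerns preventive behaviours in university students. The protocol does not say which scale the 5 refers to, so the two figures are not comparable.
- **That a correlation between domains will be inflated in the results.** The shared item would create overlap, but no such correlation is planned in the protocol.

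**Conclusion.** The key is wrong as written. It places item 38 in two domains and item 40 in none, against the protocol's own description of 40 items in four domains of 10. If it is followed, the craving/urges score is off by item 38 minus item 40: at most 4 points either way per patient per assessment, with a bias in mean change that cannot be estimated from the protocol. The 40 to 200 total is affected only if it is formed by adding the domain scores.

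The contradiction rests on the printed lists alone and needs no assumption. The consequence for the domain score assumes that the scoring follows the key literally. That the intended entry is 40 is inferred from the pattern; the adapted questionnaire, which is not shown, should confirm it. This is a minor correction.

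**What to change.** - Check the domain of items 38 and 40 against the final adapted questionnaire.
- If it confirms the pattern, change the craving/urges key to 4-8-12-16-20-24-28-32-36-40 in the protocol and in the SPSS scoring syntax.
- State that the total is the direct sum of the 40 items.
- Add a check, for every patient with complete answers, that the four domain scores sum to that total.

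The cost is one corrected item number, one sentence on the total and one line of checking syntax. The questionnaire and the data collection stay as they are.
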